8.3. Clinical Variables

The EuroSIDA study collects a comprehensive range of variables, as summarised in Table 2 below.

Table 2. Variables routinely collected in the EuroSIDA Study

Demographics and basic information	Date of birth, date first seen at department, sex, country of origin, ethnicity, height, weight, date of first HIV-1-antibody positive test, mode of HIV-1 transmission, smoking status, alcohol abuse, drug user information, predisposition to MI or stroke among relatives
Infection-related Laboratory data	HIV-ribonucleic acid ("RNA"), HCV antibody test, HCV-RNA, HBsAg result, HBV-DNA, CD4 count, CD8 count, SARS-CoV-2 PCR and antibody

Other Laboratory data	total cholesterol, HDL, LDL, haemoglobin A1c (HbA1c) and/or glucose, triglycerides, serum creatinine, ALT, AST, bilirubin, albumin, INR, platelets, haemoglobin, proteinuria
Medical treatment	All ARV start and stop dates and reasons for discontinuation (including injection site reaction and injection fatigue) and treatment for HCV, hypertension, treatment for CVD and/or diabetes, Tuberculosis treatment, opioid maintenance therapy, dyslipidaemia incl. start and stop dates
Paraclinical data	Systolic and diastolic blood pressure, liver biopsy, fibroscan, DEXA scan, plasma samples
Clinical events	Syphilis, AIDS defining events (OIs including tuberculosis), myocardial infarction, stroke, diabetes, invasive cardiovascular procedures, end-stage liver disease, end-stage renal disease, AIDS and NADMs, liver and kidney transplantation, fractures

8.3.1. Exposure definitions

The study period for data collection will start at the date of initiation of oral lead-in with CAB and/or RPV. The follow-up period for data analyses will start with first injection of CAB and/or RPV LA containing regimens and end at up to 48 months after discontinuation of the last injection.

Details about use of CAB and/or RPV LA containing regimens will be collected on a separate CRF. The data collected include dates of all planned and actual injections, use of oral bridging therapy for CAB+RPV LA, HIV subtype and resistance testing prior to initiation or at time of discontinuation of LA.

8.3.2. Outcome definitions

1.Regimen discontinuations: Discontinuation of CAB+RPV LA regimen for any reason during the study period will be captured, tabulated and reported.

Individuals who receive the oral lead-in but never initiate the CAB+RPV LA regimen will be tabulated separately but not included in the primary analysis.

Discontinuation of CAB +RPV LA will be defined as the latest date of the next scheduled injection which is missed and where bridging therapy has not been started. For example, for monthly dosing, if the first injection of CAB+RPV LA was received on June 1st, the second injection should be received on July 1st (allowed time window for second injection is June 24th to July 8th). The third injection should follow the timing of the first injection and should be received on August 1st (allowed time window for third injection is July 25th to August 8th). If not, date of discontinuation will be defined as August 8th (Monthly dosing).

For every 2 month dosing, if the first injection of CAB+RPV LA was received on June 1st, the second injection should be received on July 1st (allowed time window for second injection is June 24th to July 8th). The third injection should follow the timing of the first injection and should be received on September 1st (allowed time window for third injection is August 25th to September 8th). If not, date of discontinuation will be defined as September 8th (Every 2 month dosing).

Discontinuation will also be captured, tabulated and reported for any other CAB and/or RPV containing regimen.

Durability will be measured as proportion of individuals continuing on the regimen at the end of 6, 12 and 24 months.

Adherence will be assessed by estimating the number of individuals that missed one or more consecutive injections without taking daily oral bridging therapy or any other oral ARV regimen while not on CAB+RPV LA regimen and mean and median number of injections missed during a 12-month period. We will also estimate the number who received the injections seven or more days later than their scheduled injection visit and median duration of delayed injections in persons using bridging therapy.

In the standard follow-up data collection in EuroSIDA reasons for discontinuation are recorded as below.

Table 3. EuroSIDA – Reasons for Treatment Discontinuation

Code	Reason for Stopping Treatment
1	Treatment failure (i.e. virological, immunological, and/or clinical failure
1.1	Virological failure
1.2	Partial virological failure
1.3	Immunological failure - CD4 drop
1.4	Clinical progression
1.5	Resistance (based on test result)
2	Abnormal fat redistribution
3	Concern of cardiovascular disease
3.1	Dyslipidaemia
3.2	Cardiovascular disease
4	Hypersensitivity reaction (skin eruption etc.)
5	Toxicity, predominantly from abdomen/G-I tract
5.1	Toxicity - GI tract
5.2	Toxicity - Liver
5.3	Toxicity - Pancreas
6	Toxicity, predominantly from nervous system
6.1	Toxicity - peripheral neuropathy
6.2	Toxicity - neuropsychiatric
6.3	Toxicity - headache
7	Toxicity, predominantly from kidneys

8	Toxicity, predominantly from endocrine system
8.1	Diabetes
9	Haematological toxicity (anemia etc.)
10	Hyperlactataemia/lactic acidosis
11	Bone toxicity
15	Social contra-indication
16	Contra-indication unspecified
16.8	Contra-indication expired
16.9	Contra-indication – other
17	MTCT regimen completed
70	Pregnancy - toxicity concerns (during pregnancy)
75	Pregnancy - switch to a more appropriate regimen for PMTCT
88	Death
90	Side effects - any of the above but unspecified
90.1	Comorbidity
91	Toxicity, not mentioned above
91.1	Toxicity, unspecified
92	Availability of more effective treatment (not specifically failure or side effect related)
92.1	Simplified treatment available
92.2	Treatment too complex
92.3	Drug interaction
92.31	Drug interaction - commencing TB/BCG treatment
92.32	Drug interaction - ended TB/BCG treatment
00.00	Change in eligibility criteria (e.g. child old enough for tablets; refrigerator no longer
92.33	available)
92.4	Protocol change
92.5	Regular treatment termination (used in tblMED e.g. for DAA's against HCV, antibiotics)
92.5	End of empiric treatment
92.0	Change in treatment not due to side-effects, failure, poor adherence or contra-
92.9	indication
92.91	Change to generic drug
92.92	Change to branded drug
93	Structured Treatment Interruption (STI)
93.1	Structured Treatment Interruption (STI) - at high CD4
94	Individual's wish/decision, not specified above
94.1	Non-compliance
94.2	Defaulter
95	Physician's decision, not specified above
96	Pregnancy (see also more specific codes 70 and 75
96.1	Pregnancy intended
96.2	Pregnancy ended
97	Study treatment
97.1	Study treatment commenced
97.2	Study treatment completed

97.6	Drug not available
98	Other causes, not specified above
	Incorrect route of administration
	Injection fatigue (not related to safety)
	Injection Site Reaction
	Lost to follow-up
99	Unknown

2. Clinical effectiveness: Primary analysis for clinical effectiveness will include only those initiating the regimen per label i.e. initiating CAB+RPV LA with VL<50 copies/mL at regimen initiation. The following VL measures will be used for effectiveness assessment:

- 1. Proportion of individuals, virologically suppressed/undetectable (<50 copies/mL) at 6, 12 and 24 months following initiation of CAB+RPV LA regimen
- 2. Proportion of individuals with VL <200 copies/mL at 6, 12 and 24 months following initiation of CAB+RPV LA regimen
- 3. Proportion of individuals with confirmed virologic failure (CVF) during the first 6 months, and at 6, 12 and 24 months following initiation of CAB+RPV LA regimen defined as:
 - Two consecutive HIV RNA VL levels ≥200 copies/mL or
 - One HIV RNA VL level ≥200 copies/mL and regimen discontinuation within 4 months of VL ≥200 copies/mL

3. Resistance Testing:

Since this is a non-interventional study aiming to capture individual care in real world setting, the study will not mandate resistance testing following discontinuation of CAB+RPV LA regimen. Health care providers following the local treatment guidelines decide what laboratory and resistance tests are to be conducted. Data thus generated, including available HIV-1 subtypes, will be captured and analyzed by the study team.

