7. RESEARCH QUESTIONS AND OBJECTIVE(S)

Following the initiation of any ARV regimen containing CAB and/or RPV LA among PLWH, the study will aim to assess usage patterns, durability, discontinuation, and virologic outcomes.

The specific objectives are to:

- 1. Describe CAB and/or RPV LA containing regimens usage patterns
 - Descriptive analysis of study population by baseline demographic and clinical characteristics
 - Monitor for use of oral lead-in
 - The potential regimen combinations are listed below (Note that CAB+RPV LA is the only approved regimen)
 - a. CAB+RPV LA regimen only
 - b. CAB LA monotherapy
 - c. CAB LA use in combination with ARVs other than RPV LA
 - d. RPV LA monotherapy
 - e. RPV LA use in combination with ARVs other than CAB LA
 - f. CAB LA+RPV LA+other ARVs
 - g. Combined group b-f
- 2. Assess adherence, durability and discontinuation for persons starting CAB+RPV LA regimen;
 - Proportion of individuals discontinuing the regimens of interest will be assessed.
 - Reasons for discontinuation will be assessed.
 - Non-adherence to the dosing schedule will be assessed by:
 - a. Estimating the number of individuals that missed one or more consecutive injections without taking daily oral bridging therapy or any other oral ARV regimen while not on CAB+RPV LA containing regimens and mean and median number of injections missed during a 12-month period
 - b. Estimating the number of individuals who received the injections seven or more days later than their scheduled injection visit and median duration of delayed injections
 - c. Estimating the number of individuals who missed one or more consecutive injections without taking daily oral bridging therapy or those who received the injections seven or more days later than their scheduled injection visit (Combined group a OR b) and describe patient characteristics for the individuals that are nonadherent.
 - Number of individuals with incorrect route of administration will be described.

- 3. Assess the clinical effectiveness (i.e. proportion of individuals experiencing virologic failure) among PLWH who initiate CAB+RPV LA regimen
 - a. Estimate the proportion of individuals with virologic failure, during the first 6 months after initiation of CAB+RPV LA
 - b. Estimate the proportion of individuals with virologic failure, at 6, 12 and 24 months after initiation of CAB+RPV LA
 - c. Stratified analyses for 3a and 3b will be conducted for VL at regimen initiation (<50 copies/mL and ≥50 copies/mL).

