Descriptive analyses will compare those with and without virologic failure to assess any differences in baseline characteristics of the two groups. Detailed analysis of additional risk factors will be limited to persons with 6, 12 or 24 months of follow-up. Multivariable logistic regression models will investigate the factors associated with virologic failure at 6 months, 12 months and 24 months after CAB+RPV LA initiation. Potential explanatory variables are listed above. We will also investigate the impact of missed doses and use of oral bridging therapy by using the data collected via the CRF. Multivariate analyses will be performed when > 30 persons on CAB+RPV LA have virologic failure and analyses will be limited to persons with > 6-, 12- or 24-months follow-up. The model building strategy will follow EuroSIDA protocol and include variables significant in univariate analyses as well as *a priori* pre-specified variables of interest. Primary analysis for clinical effectiveness will include individuals on CAB+RPV LA, with VL of <50/copies/mL at regimen initiation. In addition, all the analyses will be conducted separately for individuals on CAB+RPV LA with VL of ≥50 copies/mL at regimen initiation.

Our primary analyses of virologic outcomes will censor follow-up at discontinuation of CAB+RPV LA, last visit or death, whichever occurs first, an on-treatment approach to analysis. Sensitivity analyses will use an intent to treat approach and virologic outcomes will be assessed regardless of regimen discontinuation.

We will perform additional sensitivity analysis limited to those who start CAB+RPV LA with resistance data available, to confirm no present or past evidence of viral resistance to, and no prior virological failure with agents of the NNRTI and INSTI class.

AIM 4. Monitor for resistance and next treatment response among individuals who switched off CAB+RPV LA regimen

Monitoring for resistance

Since this is a non-interventional study aiming to capture individual care in real world setting, the study will not mandate resistance testing following discontinuation of the regimen of interest. Health care providers following the local treatment guidelines decide

what laboratory and resistance tests are to be conducted. Data thus generated will be captured and analyzed by the study team.

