case of resumption of LAI after missed second injection in two months or less, we will still consider it first exposure.

Similarly, the third injection (and injections thereafter) for the two-month schedule is given two months after the second injection and hence we will allow four months after the second injection to see if the regimen was resumed (≤3 months) or re-initiated (>3 months). In case of resumption of LAI after missed third injection in three months or less, we still consider it first exposure.

Treatment with long-acting antiretroviral therapy

Which long-acting antiretroviral drugs have been initiated? (drop down menu)

1) long acting cabotegravir + long acting rilpivirine

2) long acting cabotegravir without rilpivirine

3) long acting rilpivirine without cabotegravir

Dosage: 400/600 mg (CAB) / 600/900 mg (RPV) (drop down

menu)

Date of first injection: Year/month/day

Intended dosing schedule of long-acting antiretroviral therapy Monthly/Every 2 Month

HIV resistance testing (only pops up for the first injection and if CAB + RPV has been selected)

Has a HIV resistance test been performed prior to initiation of long-acting cabotegravir + rilpivirine yes/no

If yes

Date of latest most recent resistance test prior to initiation of long-acting antiretroviral therapy Year/month/day

Method used drop down menu

Please upload a copy of the resistance test report (result will be based on central review)

(After completion of date of first injection, a new section will open for second injection with target date one month after the first injection. All the questions below refer to subsequent injections after the first)

Has the patient received the next planned injection with long-acting antiretroviral drugs yes/no

If yes, Which long-acting antiretroviral drugs were given? (drop down menu)

1) long acting cabotegravir + long acting rilpivirine

2) long acting cabotegravir without rilpivirine

3) long acting rilpivirine without cabotegravir

Dosage: 400/600 mg (CAB) / 600/900 mg (RPV) (drop down

menu)

Date of injection: Year/month/day

Intended dosing schedule of long-acting antiretroviral therapy Monthly/Every 2 Month

(if the patient switches from monthly to two-monthly injections or vice versa, a new question pops up)

Reason for switching to monthly (or 2 monthly) injection schedule (drop down menu)

- 1. Convenience
- 2. To reduce cost
- 3. To reduce side effects
- 4. Personal reasons
- 5. Other (+ text field)

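### Adding another antiretroviral while injections continue does not end CAB+RPV LA exposure under the discontinuation rule, although the protocol treats that combination as a different regimen

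*Protocol*

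**What the plan says.** Protocol section 7, Objective 1 (repeated in 8.2), lists the regimens as separate groups. The regimen of interest is "a. CAB+RPV LA regimen only". Use of a single injectable falls elsewhere, for example "b. CAB LA monotherapy", and both injectables with added drugs are "f. CAB LA+RPV LA+other ARVs". The protocol notes that only the first of these is approved.

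Section 8.3.2 opens its outcome definitions with "Discontinuation of CAB+RPV LA regimen for any reason during the study period will be captured, tabulated and reported". It then says what discontinuation is: "Discontinuation of CAB +RPV LA will be defined as the latest date of the next scheduled injection which is missed". That sentence ends with a bridging condition ("which is missed and where bridging therapy has not been started"). The worked examples that follow, for monthly and two-monthly dosing, concern injection dates only.

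Three results depend on this rule:
- **Durability** (8.3.2): the share still on the regimen at 6, 12 and 24 months.
- **On-treatment virologic analysis** (8.6, Aim 3): "Our primary analyses of virologic outcomes will censor follow-up at discontinuation of CAB+RPV LA, last visit or death, whichever occurs first".
- **Confirmed virologic failure, second criterion** (8.3.2): one viral load ≥200 copies/mL plus discontinuation within 4 months of it.

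The case report form (Annex 1) asks at each later visit whether the planned injection was received. Under yes comes "If yes, Which long-acting antiretroviral drugs were given? (drop down menu", and the answers include either injectable without the other. Questions on bridging, restarting and reasons for stopping open only under no.

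**The concern.** The exposure is defined by its drug content (these two injectables and nothing else), but its end is defined by injection attendance. The two do not match. A person can move from group a to group f without missing an injection, and the rule does not register the move.

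An antiretroviral might be added after a raised viral load. If it is, and the person then re-suppresses on the enlarged regimen, the primary analysis credits that result to CAB+RPV LA alone. The same person counts towards durability and may drop out of the failure count. Each of these shifts favours the regimen.

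The intent-to-treat sensitivity analysis assesses outcomes regardless of discontinuation, so it does not set these people apart either. Section 8.6 expects few primary endpoints, so a handful of misclassified people could be visible in the failure proportion.

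**Working it through.** No figure in the protocol is at issue, so the check traces the rule first and adds an illustration of size afterwards.

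**1. A person who adds an antiretroviral and keeps every injection**

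| Step | Rule | Result |
|---|---|---|
| Regimen at start | Section 7, group a | CAB+RPV LA only |
| Regimen after the addition | Section 7, group f | A different group |
| Discontinuation date | 8.3.2: missed injection, no bridging | None; nothing was missed |
| Durability | 8.3.2: still on the regimen | Counted as continuing |
| On-treatment analysis | 8.6: censor at discontinuation, last visit or death | Not censored by the addition |
| Failure, criterion 1 | Two consecutive viral loads ≥200 | Not met if the next value is <200 |
| Failure, criterion 2 | One viral load ≥200 plus discontinuation within 4 months | Not met unless an injection is also missed in that time |

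This follows directly from the wording. People with two consecutive values ≥200 are caught by criterion 1 whatever they add, so only single raised values followed by a value below 200 escape.

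**2. A person who receives one injectable only at a scheduled visit**

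- Section 8.3.2 speaks of the scheduled injection of CAB+RPV LA. If one component is absent, that injection can be read as missed and the rule applies.
- Annex 1 enters the same visit under received: yes, so the discontinuation branch stays closed. A change of dosing schedule prompts a reason question; dropping a drug does not.
- The two places therefore support different answers, and the text does not choose.

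**3. Illustration of size**

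The protocol gives no rate of modification without a missed injection. I assume 1%, 2% and 5% of starters, for illustration only. The base rows are Table 4 at N=500: 10% (0.075–0.13) and 2% (0.01–0.036). Exact Clopper-Pearson limits reproduce both: 0.0751–0.1297 for 50/500 and 0.0096–0.0365 for 10/500.

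Counting modifiers as having left the regimen adds 500 × m people:

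| m (assumed) | Added | Discontinued or modified | Failure, upper bound |
|---|---|---|---|
| 0 | 0 | 50/500 = 10% (7.5–13.0%) | 10/500 = 2% (1.0–3.6%) |
| 1% | 5 | 55/500 = 11% (8.4–14.1%) | 15/500 = 3% (1.7–4.9%) |
| 2% | 10 | 60/500 = 12% (9.3–15.2%) | 20/500 = 4% (2.5–6.1%) |
| 5% | 25 | 75/500 = 15% (12.0–18.4%) | 35/500 = 7% (4.9–9.6%) |

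The failure column is an upper bound. It takes every modifier to have had one viral load ≥200 within 4 months before the change and not to be counted as a failure already. The discontinuation column takes no modifier to miss an injection later within the same horizon.

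**The case against.** The strongest reply has four parts.

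**The protocol captures discontinuation for any reason and collects every antiretroviral date.** This is true, but the any-reason sentence and the Table 3 codes cover why treatment stopped, not what counts as stopping a two-drug-only regimen. The dates in Table 2 make a repair possible, but the definition does not use them.

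**The missed-injection sentence is only a dating convention, and concurrent drugs can be left to the analysis plan.** This stands only in part. The analysis plan is not at hand and may address the point. But the protocol itself fixes the definition, and an analysis plan that follows it inherits the gap.

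**A one-injectable visit is already a missed CAB+RPV LA injection.** This reading is fair. A reader might infer that anyone who drops one injectable is certainly kept on the regimen; the documents do not support that. The case report form is a data-entry branch, and it does record which drugs were given. What remains is an ambiguity to settle.

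**Calling every added drug a discontinuation would do harm.** This stands. Aim 4 follows people who have switched off CAB+RPV LA, and 8.3.1 runs follow-up from discontinuation of the last injection. People still receiving both injectables do not belong there, so the repair must keep modification and stopping apart.

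On off-label use, 8.6 describes those users at initiation, but Aim 5 is meant to monitor adherence to the label and Aim 2 covers usage patterns. Later moves to groups b–f are not excluded; the protocol does not say that they will be counted.

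**Conclusion.** The point holds for antiretrovirals added during continued injections: the rule as written keeps these people on CAB+RPV LA for durability, for on-treatment censoring and for the second failure criterion. For visits with one injectable, the finding is an unresolved ambiguity between 8.3.2 and Annex 1.

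The direction favours the regimen. The size cannot be determined from the document and may be small. A reader might suppose that 1–3% of starters modify the regimen and that half do so after a viral load ≥200. That would imply failure understated by 0.5–1.5 points. At N=500 and 3% failure, the standard error is √(0.03 × 0.97/500) = 0.76 points, so the shift would be 0.7–2.0 standard errors. The documents support neither the rate nor the half. The top of that range would also need 1.5/3 = half of all failures to be people of this kind. The protocol does not say how often drugs are added after viraemia. These figures and the table above show sensitivity only; they are not estimates of bias.

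**What to change.** In 8.3.2, define an analysis end date for CAB+RPV LA-only exposure as the earliest of:
- the missed-injection date as now defined;
- the first scheduled visit at which only one injectable is given;
- the start of another antiretroviral alongside continued injections, oral bridging excepted.

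Then:
- Use this date for durability and for on-treatment censoring.
- Count a modification within 4 months of a viral load ≥200 under the second failure criterion, or report confirmed failure with and without it.
- Report modifications separately from full discontinuation.
- Keep Aim 4 follow-up tied to stopping the injections, consistent with 8.3.1.
- Under Aim 5, tabulate later moves from group a to groups b–f as well as starts.

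This changes an analysis definition only and says nothing about how anyone should be treated. The cost is slightly lower reported durability and slightly more analysis work. The drugs given at each injection (Annex 1) and all antiretroviral start and stop dates (Table 2) are already collected. Because the case report form asks for a reason only when an injection is not given, its reason-for-discontinuation entry would be absent for modifications, which is a further reason to report them on their own line.

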8.6. Data analysis

Between 5-10 EuroSIDA participating clinics (of 100 clinics) have a viral load measured with a limit of detection of >50 copies/ml. Individuals starting CAB+RPV LA regimen with a viral load limit of detection >50 copies/ml will be excluded from primary analyses for clinical effectiveness. We will summarise data for all other users and compare them to those included for generalisability and to help interpret the data.

AIM 1. Describe CAB and/or RPV LA containing regimens usage patterns

New users of CAB and/or RPV LA containing regimens aged >18 years will be characterized using demographics, clinical, immunologic and virologic characteristics at baseline (i.e. at initiation of regimen) stratified by different regimens noted in groups a-g above.

Individual characteristics and baseline covariates will be described using median (interquartile range [IQR]) values for continuous data and relative frequencies for categorical data. Characteristics of those starting different CAB and/or RPV LA containing regimens will be compared using chi-squared tests for categorical variables and non-parametric tests for continuous variables.

Those who start oral lead in but do not start LA regimen will be tabulated separately and demographics will be described.

AIM 2. Assess adherence, durability and discontinuation for persons starting CAB+RPV LA regimen

Individuals who receive the oral lead-in but never initiate the CAB+RPV LA regimen will be tabulated separately but not included in the primary analysis. Reasons for discontinuation will be assessed using the reasons for discontinuation as reported to EuroSIDA.

Treatment and regimen usage patterns of CAB+RPV LA regimen will be described using frequency distributions while duration of continuous treatment will be described using the mean, median, range, and standard deviation. Number of individuals with incorrect route of administration will be described.

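### The +7-day discontinuation rule in 8.3.2 has no clause for resumption, while the case report form keeps un-bridged resumers in the same exposure; this distorts discontinuation, durability and the on-treatment analysis

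*Protocol*

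**What the plan says.** **Discontinuation (Protocol 8.3.2).** It is "defined as the latest date of the next scheduled injection which is missed and where bridging therapy has not been started". In the two-month example the first injection is on June 1st and the third is due on September 1st: "allowed time window for third injection is August 25th to September 8th", and then "If not, date of discontinuation will be defined as September 8th (Every 2 month dosing". The monthly example has the same structure: "If not, date of discontinuation will be defined as August 8th (Monthly dosing". Neither example says what happens if the person is injected after the window closes.

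**Case report form (Annex 1).** A planned injection not given and not bridged is a scenario of its own, with later resumption as one of its outcomes. For the two-month schedule, resumption after a missed second injection counts as the same exposure up to 2 months. For the third and later injections: "In case of resumption of LAI after missed third injection in three months or less, we still consider it first exposure". The form asks for a reason for discontinuation only where the answer on restarting is no. No resumption limit is given for monthly users.

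**Virologic analysis (8.6, Aim 3).** "Our primary analyses of virologic outcomes will censor follow-up at discontinuation of CAB+RPV LA, last visit or death", whichever is first. A sensitivity analysis by intent to treat disregards discontinuation. The same section adds: "We will also investigate the impact of missed doses and use of oral bridging therapy".

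**Other users of the discontinuation date.** Durability is the proportion still on the regimen at 6, 12 and 24 months (8.3.2). One limb of confirmed virologic failure is a single viral load of at least 200 copies/mL plus discontinuation within 4 months (8.3.2). Aim 4 counts 12, 24, 36 and 48 months from discontinuation.

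**The concern.** A person injected on day 8 without bridging is discontinued under 8.3.2 and, on the two-month schedule, still in the first exposure under Annex 1. The adherence outcomes (injections missed in 12 months, injections seven or more days late) also assume that people remain on the regimen after a late or missed dose.

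Five results depend on which rule is applied:

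- the discontinuation proportion, and the table of reasons, because the form requests no reason from resumers;
- durability at 6, 12 and 24 months;
- the primary on-treatment analysis, which closes at the first un-bridged miss although section 6.2 gives the effect of non-adherence on failure as part of the study's rationale;
- confirmed virologic failure, through its discontinuation limb;
- the Aim 4 clock, which would start in people still receiving the injections.

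**Working it through.** **1. Reproduce the plan's dates.** Due dates of July 1, August 1 and September 1, each ± 7 days, give June 24 to July 8, July 25 to August 8 and August 25 to September 8. These match 8.3.2. The rule is therefore due date + 7 days.

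**2. Length of the conflict on the two-month schedule (first injection June 1).** Annex 1 does not say where its 2 and 3 months start, so both readings are shown.

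- Second injection, due July 1, discontinued July 8 under 8.3.2. Two months from the first injection ends August 1: 31 days late, 24 days of conflict. Two months from the missed date ends September 1: 62 days late, 55 days of conflict.
- Third injection, due September 1, discontinued September 8. Three months from the second injection ends October 1: 30 days late, 23 days of conflict. Three months from the missed date ends December 1: 91 days late, 84 days of conflict. That second reading runs past Annex 1's own four-month look-forward, which ends November 1 (54 days of conflict).

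**3. Direction for discontinuation and durability.** Anyone with an un-bridged miss who fails to resume within the Annex 1 limit is also discontinued under 8.3.2. The reverse is not true: those who resume between day 8 and the limit are discontinued under 8.3.2 only. The 8.3.2 count is therefore never lower, and durability never higher.

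**4. Overlap with lateness.** Late means day 7 or later; discontinued means not injected by day 7. Without bridging, the only injection that is late and not a discontinuation is one given exactly on day 7.

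**5. Missed doses in the on-treatment analysis.** Censoring falls at the end of the first missed window. A person contributes at most one un-bridged miss and no viral load after it. The Aim 3 models are also limited to people with more than 6, 12 or 24 months of follow-up. If that means censored follow-up, someone with an earlier un-bridged miss leaves the model altogether.

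**6. Confirmed virologic failure, two opposite effects.** A rebound measured after day 7 of the gap falls after censoring and is lost. Conversely, one viral load of at least 200 followed within 4 months by an injection 8 days late satisfies the discontinuation limb, even if the person resumed and re-suppressed.

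**7. Illustrative size, two-month users.** Let q be the chance that a scheduled injection is un-bridged, more than 7 days late and later resumed. The documents do not give q; 0.5% to 2% is assumed. Injections after the first fall at months 1, 3, 5 and so on, so k = 6 by 12 months and k = 12 by 24 months. With independent misses, the share of true continuers labelled discontinued is 1 − (1 − q)^k:

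- q = 0.5%: 1 − 0.995^6 = 3.0%; 1 − 0.995^12 = 5.8%
- q = 1%: 1 − 0.99^6 = 5.9%; 1 − 0.99^12 = 11.4%
- q = 2%: 1 − 0.98^6 = 11.4%; 1 − 0.98^12 = 21.5%

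If true stopping by 12 months were 10% (also assumed), apparent stopping would be 1 − 0.90 × (1 − q)^6 = 12.7%, 15.3% and 20.3%. Because (1 − q)^k is convex in q, clustering of misses in the same people at the same average rate lowers all these shares.

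**The case against.** **The two rules may do different jobs.** 8.3.2 can be read as dating a stop already established by other means, and the Annex 1 limits as fixing the boundary of the first exposure (the inclusion rule in 8.2) without saying that a resumer counts as continuing for durability. That reading is possible. Against it, both examples make the missed window itself the trigger, and no clause excludes resumers. At best the text is ambiguous on a main outcome, and a programmer following it literally would label resumers as discontinued.

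**Later viral loads are not lost to the study.** This stands. The intent-to-treat sensitivity analysis keeps them, bridged misses stay in the on-treatment analysis, and Aim 4 lists missed and delayed doses as explanatory variables for resistance. A reader might infer that missed doses cannot be studied at all; the documents do not support that. The loss concerns un-bridged misses in the primary analysis. The sensitivity analysis is only a partial remedy: it mixes resumers with people who switched for good, and it does not touch discontinuation or durability.

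**Failure is not simply under-counted.** A reader might infer that from the censoring. The discontinuation limb works the other way, so the net direction is unknown.

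**The size is assumed.** This stands too. A similar percentage for monthly users is tempting, but Annex 1 gives them no resumption limit, so mislabelling has no reference standard there.

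**Duration of treatment.** A reader might add that "duration of continuous treatment will be described using the mean, median, range, and standard deviation" ignores ongoing users. That is a separate, descriptive matter often settled in an analysis plan, and it forms no part of this point.

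**Conclusion.** The point holds as a contradiction between 8.3.2 and Annex 1 that carries into 8.6.

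- **Certain from the text:** relative to the Annex 1 rule on the two-month schedule, 8.3.2 can only raise discontinuation and lower durability. Nearly all un-bridged late injections become discontinuations. The Aim 4 clock can start in people still on the regimen.
- **Certain for the primary on-treatment analysis only:** follow-up stops at the first un-bridged miss, so the effect of such misses can hardly be assessed there.
- **Unknown:** the net effect on confirmed virologic failure, and the size of the distortion overall. The 5.8% to 21.5% of two-month users by 24 months rests on an assumed 0.5% to 2% per injection and on independence, and is lower if misses cluster.

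Which gap length ought to count as stopping is not judged here. The sections need reconciling before the outcomes are derived.

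**What to change.** Reconcile 8.3.2, 8.6 (Aim 3) and Annex 1 with one definition, for analysis only, using mutually exclusive states:

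1. late but resumed within the reconciled limit: on regimen, counted as non-adherent;
2. bridged;
3. discontinued: a recorded stop or switch, or no resumption within the limit.

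State the date from which the limit runs, and state a limit for monthly users. In the on-treatment analysis, keep viral loads during a gap up to resumption, switch to another regimen or the end of the limit, whichever comes first. Stopping at a switch matters: otherwise results on the next regimen would be credited to CAB+RPV LA. Use the same definition for the discontinuation limb of confirmed virologic failure and for the start of the Aim 4 clock. Report the +7-day rule as a sensitivity analysis.

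**Cost.** Protocol wording and derivation code; no patient's care changes. Planned and actual injection dates are already collected (8.3.1). Annex 1 collects injections only to 24 months plus six weeks, so the chosen limit should be checked against that. On the longest reading, a miss at month 23 has a limit ending at month 26, beyond about 25.4 months. The downside is that discontinuation status becomes known slightly later.
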